TITLE OF THE PROJECT: DEMENTIAS AND MICROBIOTA
COMPOSITION: MICROBIOTA COMPOSITION IN DEMENTIAS. IS
POSSIBLE TO REVERT THE DEMENTIA SYMPTOMS
REVERTING THE MICROBIOTA COMPOSITION?
TITLE OF THE PROJECT (ACRONYM): DEM-BIOTA

PI: [name]

NCT number: *Pending evaluation*

Study Protocol and Statistical Analysis Plan: Version- June 1, 2023

METHODOLOGY

Scientific programme and project organization

[figure not shown]
The overall concept of the DEM-BIOTA project is organized into 4 main work packages (WPs). The approach is based on a complete integrated assessment of the different major dementias in relation to microbiota composition and a clinical trial using probiotic mixture that tries to restore the microbiota in order to reverse dementia symptoms. The results will be applied to the dementias treatment, being an important contribution to the nowadays knowledge in general and in our country.

WP1.- Protocol revision and preparation

This WP aims to revise all the information for the protocols, update the latest information into protocols and write them. These protocols should be aligned with the hospitals' procedures. Also write all the information that will be provided to the patients to collect the samples and prepare all the tests and scales to be administered. To achieve this objective, the following tasks are defined:

Task 1.1. Protocol and tests revision and protocol redaction

PhD and Postdoctoral grants: The vacant for the postdoctoral student and predoctoral student will be arranged and announced at the beginning of this period. We will expect to incorporate the Postdoc the lasts months of 2020 to be able to participate from all the WP1 tasks.

Scheme of the DEM-BIOTA project summarizing the Work Packages (WP) of the project and their relationships.

Protocols preparation: For the revision and update of all the procedures, a bibliographic revision will be done. The protocols will be updated with the latest scientific information in order to include any new aspect that can improve the studies. For the neuropsychological tests and scales, a revision of any new aspect published related to them will be done and incorporate to the neuropsychological assessment. We will contact the laboratory analysis to confirm all the aspects related with the collection of the stool samples and write the protocols related to them.

Alignment with hospitals' procedures: All the protocols will be presented to the hospitals and decide if there is any aspect that does not fit with the hospitals procedure and align to them, in order to fit the procedure protocol with all the procedures of the hospitals involved.

Task 1.2. Final protocol presentation to the Ethical Committee of Clinical Research with Medicines (CEICm)

Apply for CEICm authorization: The project will be written in a specific template and presented to the Ethical Committee of Clinical Research with Medicines (CEICm) of the Institut d'Investigació Sanitària Pere Virgili (IISPV), since it is the Ethical Committee of reference to our center. When authorization is available, the study will be able to begin.

Risks and solutions envisaged for task 1.2: Risk: negative resolution. Contingency: modify the aspects that they pointed to not accept the project and apply again. This can delay us one or two months at most and we still were on time to achieve the objectives and the project. In this sense we have already dealt with similar situations requesting the approval of the aforementioned committee, with always reaching a positive resolution.

Task 1.3. Publicity of the study to enroll participants

Publicity of the study will be done (flyers, posters, etc.) and will be disseminated in all the hospitals involved. All the neuropsychologist and neurologist of the participant hospitals will have the study information and the informed consent (for the first study) ready to give to the target patients.

WP2.- Dementias and microbiota

To evaluate the relationship between dementias and their features with microbiota composition it is important to make a deep assessment of these features and control possible influencing variables as Mediterranean diet and lifestyle adherence, stressful events and cognitive reserve. A deep interview about medication and other illnesses will be conducted. Individual and sociodemographic data will be also collected.

The general objective of WP2 is to study the microbiota composition of the most known dementias: Alzheimer Disease (AD), Parkinson Disease Dementia (PDD), Lewy Bodies Dementia (LBD), Frontotemporal Dementia (FTD)-behavioral variant, comparing them to healthy control subjects in relation to their neuropsychological, neuropsychiatric and functional state.

The following tasks will be carried out in this WP:

Task 2.1. Patients recruitment

We will recruit a total of 150 patients, 30 AD, 30 PD, 30 DLB, 30 FTD-behavioral variant and 30 Mild Cognitive Impairment (MCI) patients. This sample size is enough to detect differences in gut microbiota with sequencing technics (Vogt et al, 2017). The criteria for the recruitment will be:

Inclusion criteria: AD, PD, DLB, FTD-behavioral variant or MCI-amnesic variant diagnosed by the neurology service; more than 60 years.

Exclusion criteria: Comorbidity with other significant neurology disease, infectious treatment with antibiotics in the previous 6 months prior to providing the stool sample, corticosteroid use, immunosuppressors or immunostimulants treatment, illnesses of the gastrointestinal (GI) tract, large doses of commercial probiotics consumed (greater than or equal to 10^8 colony forming units (cfu) per organisms per day).

The hospitals will have publicity of the study and when target patients are attended by the neurologists/neuropsychologist (group research members) will be informed of the study and encourage to enroll. If the patients agree to enroll the study, they (or legal tutor) will sign the informed consent and give their contact telephone number to be able to contact again. The neurologists/neuropsychologist also will give them the stool collection pack, to be kept for them until the contact of the research team for the interview.

Risks and solutions envisaged for task 2.1: Risk: patient lost from the recruitment until the interview, fail in neuropsychological assessment or fecal collection. Contingency: the sample size to detect differences in the literature were 25 subjects (Vogt et al, 2017) and we will recruit 30, 5 more of each group to ensure the results.

Task 2.2. Healthy controls recruitment

We will recruit a total of 30 healthy control volunteers. The criteria for the recruitment will be:

Inclusion criteria: more than 60 years. Exclusion criteria: Significant neurology disease diagnosed, infectious treatment with antibiotics in the previous 6 months prior to providing the stool sample, corticosteroid use, immunosuppressors or immunostimulants treatment, illnesses of the gastrointestinal (GI) tract, large doses of commercial probiotics consumed (greater than or equal to 10^8 colony forming units (cfu) per organisms per day).

This control group were recruited from relatives of the patients enrolled or general population and interviewed at the hospital (relatives, University or their homes).

Task 2.3. Citation of the volunteers, assessment and stool sample collection

Volunteers were contacted and cited for an interview (at the same hospital or at home, the more comfortable to them). In order to obtain the stool sample, the researcher will explain the instructions (a paper with the written instructions will be with the kit too) and encourage to collect 1-2 days before the interview and keep in the freeze until they deliver us in the interview.

The stool collection kit will be a special kit that preserved Nucleic Acid even at room temperature over 2 years for Deoxyribonucleic acid (DNA) and up to 7 days for RNA, so no need immediately processes samples (Stool collection and preservation system, Norgen, Biotek Corporation, Canada).

At the time of the interview, the volunteer will come accompanied and give the stool sample in the saving tube of the collection kit.

The assessment will include:

- Patient identification, sex, age, level of education, years of schooling, weight and height and diagnostic (others sociodemographic data) and revision of the inclusion/exclusion criteria
- Medication, diseases (diabetes, cholesterol, hypertension, etc.)

-Tests/scales:

- Mediterranean lifestyle index interview (MEDLIFE), (Sotos-Prieto, et al, 2015), MEDLIFE will give us information about how the patient follow Mediterranean diet and habits;
- Live Events Questionnaire-Cuestionario de sucesos vitales (CSV), (Sandín & Chorot, 2017), CSV the information about successful stress events that could affect and modify the main relations of the study
- Screening cognitive tests/scales: Mini Mental State Examination (MMSE) (Folstein et al, 1975), Global Deterioration Scale-Functional Assessment Staging (GDS-FAST) (Reisberg, 1982, 1988), Clinical Dementia Rating (CDR) (Hughes, 1982)
- Cognitive Reserve scale (León-Estrada et al, 2017)
- Activities of Daily Living (ADLs) and Neuropsychiatric scale (Test Barcelona-2), (Peña-Casanova, 2019)
- Anxiety and Depression Scale (Goldberg et al 1988)
- Memory Impairment Screen (MIS) (Buschke et al, 1999)
- Categorical evocation fluency (Test Barcelona-2), (Peña-Casanova, 2019)
- Temporary orientation (Test Barcelona-2), (Peña-Casanova, 2019)
- Free and Cue Selective Reminding Test (FCSRT) (Buschke, 1984)
- Trail Making Test (TMT) A and B (Reitan, 1958)
- Abbreviated Boston evocation test (Kaplan et al, 2001)
- Verbal span and constructive praxis (Test Barcelona-2), (Peña-Casanova, 2019)
- Clock test (Shulman, 2000)
- Spatial and personal orientation (Test Barcelona-2), (Peña-Casanova, 2019)
- Frontal Assessment Battery (FAB), (Dubois et al, 2000)

This assessment will allow not only to obtain the cognitive level, also better describe the different functional cognitive areas, detect and describe neuropsychiatric symptoms and obtain a good index of functionality with a novel high reliability and validity scale of ADLs (Torrente M, 2018; Peña-Casanova et al, 2019).

Task 2.4. Stool samples saving

The samples will be collected by the researchers from the volunteers and kept at Medicine Faculty at -80°C, until their analysis by a specialized and experimented laboratory. In the Faculty of Medicine at Universitat Rovira i Virgili, our researcher group has available some freezers where the stool samples where will be kept at -80°C until sending them to the laboratories to be analyzed.

Risks and solutions envisaged for task 2.1: Risk: loss of electricity in freezers. Contingency: In Medicine faculty there is an emergency electricity generator to keep the samples of all the researchers

Task 2.5. Stool samples shipment to laboratory analysis

Once the recruitment was finished the samples will be sent to the analyzer laboratory with special shipment with liquid nitrogen (that our researcher group is used to do). The shipment will be coordinated at every moment with the laboratory and the shipping company.

Task 2.6. Obtainment of the data and statistical analysis

The fecal samples will be analyzed by Sequencing Technics and characterize their bacterial taxonomic composition. These data will be received within 2-3 months after the samples reach the analyzer laboratory. Statistical analysis with microbiota data and all other data collected will be done. All the descriptive for all the data collected will be calculated for each group. Microbiota data from different dementias will be compared to control volunteers and between the different groups, also within the results of all the assessments. AD microbiota composition will be compared to that described in scientific literature from other countries. Multivariable analysis will be also done to try to describe the variables associated with each dementia but taking into account the sample size in order to extract conclusions in this sense.

At the moment of statistical analysis, a methodology specialist will be asked to revise them and decide if any other analysis could be done in order to better analyze the data

Risks and solutions envisaged for task 2.6: Risk: data loss. Contingency: In order to ensure no data loss, a periodical back up will be carried out.

WP3.- Probiotic effects on AD dementia

The objective of this WP is to enhance the knowledge of the potential positive probiotic effects in the gut composition and on their clinical symptoms of the Alzheimer disease patients. In this sense our group has already done studies of the beneficial effects of the PNU-282987, an alpha 7 nicotinic receptor agonist in an animal model of Alzheimer's disease, with positive results in anxiety symptoms but not in cognitive (Vicens et al, 2013a, 2013b, 2017).

It is generally agreed that probiotic strains should be of host origin with a beneficial effect on the host, withstand into food stuff with a high count of them, withstand transits through intestine and colonize lumen of the tract, produce antimicrobial agents, and be technologically appropriate for industrial production (Shewale et al., 2014). Due to the lack of evidence about the appropriate dosage of probiotics for AD, we used the below-mentioned doses based on few previous studies in healthy subjects (Benton et al., 2007; Mohammadi et al., 2015) and on AD patients with positive results (Akbari et al 2016).

To achieve this objective, the following tasks will be carried out in this WP:

Task 3.1. Patients recruitment and assignment to experimental groups

We will recruit a total of 60 AD patients, 30 will ingest the probiotic mixture and 30 will ingest placebo (randomized assignment to the groups will be done). The experimental group will take the probiotic ingest daily: *Lactobacillus acidophilus*, *Lactobacillus casei*, *Bifidobacterium bifidum*, and *Lactobacillus fermentum* (2×10^9 CFU/g of each). This mixture of bacteria has been showed to have positive results with 12 weeks treatment (Akbari et al, 2016). The duration of the treatment will be 24 weeks, with two posttreatment assessment, at 12 weeks and at 24 weeks.

To calculate sample size, we used the standard formula suggested for clinical trials by considering type one error(a) of 0.05 and type two error(b) of 0.20 (power = 80%) based on a previous study (Akbari et al, 2016). We used 1.3 as SD and 1.1 as the difference in mean (d) of MMSE as key variable. Accordingly, we needed 25 persons in each group. Assuming 5 dropouts in each group, the final sample size was determined to be 30 persons per group. This sample size is enough to detect differences in cognitive performance due to a probiotic treatment (Akbari et al, 2016).

The criteria for the recruitment will be: Inclusion criteria: AD diagnosed by the neurology service; more than 65 years. Exclusion criteria: Comorbidity with other significant neurology disease, infectious treatment with antibiotics in the previous 6 months prior to providing the stool sample, corticosteroid use, immunosuppressors or immunostimulants treatment, illnesses of the GI tract, large doses of commercial probiotics consumed (greater than or equal to 10^8 cfu per organisms per day).

The hospitals will have publicity of the study and when target patients were attended by the neurologists/neuropsychologist (group research members) will be informed of the study and encourage enrolling. Also, neuropsychologists of the Alzheimer's Association will inform of the study and encourage enrolling. In the Alzheimer stimulation center of Alzheimer Association come regularly about 60-70 patients. If the patients agree to enroll the study, they (or legal tutor) will sign the informed consent and give their contact telephone number to be able to be contacted again. The neurologists/neuropsychologist also will give them the stool collection pack, to be kept for them until the contact of the research team for the interview.

Risks and solutions envisaged for task 3.1: Risk: patient lost from the recruitment until the interview, fail in neuropsychological assessment, fecal collection or treatment adherence. Contingency: we will recruit some more patients of each group 5-10 patients.

Task 3.2. Citation of the volunteers before the probiotic intake period: assessment, stool sample collection and treatment initiation

Volunteers were contacted and cited for an interview (at the same hospital, center Alzheimer's Association or at home, the more comfortable to them). In order to obtain the stool sample, the researcher will explain the instructions (a paper with the written instructions will be with the kit too) and encourage to collect 1-2 days before the interview and keep in the freeze until they deliver us in the interview (stool collection and preservation system, Norgen, Biotek Corporation, Canada).

At the time of the interview, the volunteer will come accompanied and give the stool sample in the saving tube of the collection kit.

The assessment will include:

-Patient identification, sex, age, level of education, years of schooling, weight and height and diagnostic (others sociodemographic data) and revision of the inclusion/exclusion criteria

-Medication, diseases (diabetes, cholesterol, hypertension, etc)

-Tests/scales:

-Mediterranean lifestyle index interview (MEDLIFE), (Sotos-Prieto, et al, 2015), MEDLIFE will give us information about how the patient follow Mediterranean diet and habits;

-Live Events Questionnaire-Cuestionario de sucesos vitales (CSV), (Sandín & Chorot, 2017), CSV the information about successful stress events that could affect and modify the main relations of the study

-Screening cognitive tests/scales: Mini Mental State Examination (MMSE) (Folstein et al, 1975), Global Deterioration Scale-Functional Assessment Staging (GDS-FAST) (Reisberg, 1982, 1988), Clinical Dementia Rating (CDR) (Hughes, 1982)

-Cognitive Reserve scale (León-Estrada et al, 2017)

-Activities of Daily Living (ADLs) and Neuropsychiatric scale (Test Barcelona-2), (Peña-Casanova, 2019)

-Anxiety and Depression Scale (Goldberg et al 1988)

-Test Barcelona-2 battery, beta abbreviated version (Peña-Casanova, 2019), we will use Test Barcelona-2 battery to an extensive and deep neuropsychology assessment.

The patients were requested not to change their ordinary physical activity and not to take any nutritional supplements during the 12-week trial. The researcher will give to the volunteer in this meeting the treatment to take from the day after the interview until 12 weeks after and a new stool collection kit (in order to bring another stool sample, the next interview day, after 12 weeks).

Task 3.3. Citation of the volunteers after the probiotic intake period: assessment and stool sample collection

There will be two assessments after 12-week treatment period and 24-week treatment period. At the time of the interview, the volunteer will come accompanied and give the stool sample in the saving tube of the collection kit. The assessment will be the same that in task 3.2.

The researcher will give to the volunteer in the 12-week meeting the treatment to take from the day after the interview until 12 weeks after and a new stool collection kit (in order to bring another stool sample, the next interview day, after 12 weeks).

Task 3.4. Stool samples saving

Same as task 2.4.

Task 3.5. Stool samples shipment to laboratory analysis

Same as task 2.5.

Task 3.6. Obtainment of the data and statistical analysis

The fecal samples will be analyzed by Sequencing Technics and characterize their bacterial taxonomic composition. These data will be received within 2-3 months after the samples reach the analyzer laboratory.

Statistical analysis with microbiota data and all other data collected will be done. All the descriptive for all the data collected will be calculated for each group. Microbiota data from experimental groups and the results of the assessments will be compared (Student's t-test and Pearson Chi-square test). Multivariable logistic regression analyses will be done to relate microbiota composition and results of the neuropsychological assessment.

At the moment of statistical analysis will be ask a methodology specialist to revise them and decide if any other analysis could be interesting to do.

Risks and solutions envisaged for task 3.6: Risk: data loss. Contingency: In order to ensure no data loss, a periodical back-up will be carried out.

WP 4.- Dissemination and formation

This WP aims to effectively disseminate our results in international conferences, publishing the results in international scientific journals of high impact factor (1Q-2Q) and disseminate to the benefit society directly as well as educate of the benefits of the variables studied and resulted positive, e.g. the Mediterranean lifestyle, probiotic consumption etc. To achieve this objective, the following tasks will be carried out in this WP:

Task 4.1. Attendance and presentation of communications to congresses

Most of the University research group will search for the most important International Congresses of the study area and attend to them presenting preliminary results (European congresses that will take place between 24 and 44 months, e.g. FENS forum, Alzheimer's Association International Conference, etc).

Task 4.2. Publish articles in high impact Scientific Journals Open access

Research group will make the most in order to publish the results of the project studies in high impact Scientific Journals in open access.

Task 4.3. Advertising in magazines, newspapers, radio, TV and conferences to the general and target public

Research group will contact publishing department of magazines, newspapers, radio, TV and organize together with the University, Hospitals, Alzheimer's Association and Local Governments some conferences both to general public and target public. The results of the studies will also be published, at least, in the University, Hospitals, Alzheimer's Association and Tecnatox webs. Tecnatox center will share the results with all the partners around the world.

Task 4.4. Inform patients, other professionals related and educate general public about the results of the project

We will make a flyer to distribute in hospitals and other public places about the results of the project and recommendations to adapt to keep good health and offer us to hospitals, public centers and local government to make educational talks to general public.

Clinical professionals of the research group will inform their patients about the potential risks and benefits of the probiotic compound.

References

- Buschke H (1984). Cued recall in amnesia. *Journal of Clinical Neuropsychology*, 6:433-40.

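### WP2 healthy controls need no evidence of normal cognition, so people with undiagnosed impairment can enter the single reference group, although CDR and MMSE are already measured

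*Combined protocol and SAP*

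**What the plan says.** The WP2 objective is to describe the microbiota of the main dementias, "comparing them to healthy control subjects in relation to their neuropsychological, neuropsychiatric and functional state". Task 2.1 recruits 30 patients in each of five groups (four disease groups and amnesic MCI), all diagnosed by a neurology service.

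For controls, Task 2.2 states "We will recruit a total of 30 healthy control volunteers" and gives the criteria: "Inclusion criteria: more than 60 years. Exclusion criteria: Significant neurology disease diagnosed". The remaining exclusions match those for patients and are not cognitive: "infectious treatment with antibiotics in the previous 6 months prior to providing the stool sample, corticosteroid use, immunosuppressors or immunostimulants treatment, illnesses of the gastrointestinal" disease, and high-dose probiotics. On their source it says "This control group were recruited from relatives of the patients enrolled or general population".

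One battery serves everyone under "Task 2.3. Citation of the volunteers, assessment and stool sample collection". It has a group of instruments headed "Screening cognitive tests/scales: Mini Mental State Examination (MMSE"), which also contains the GDS-FAST and the CDR. No cut-off is attached to any of them. The interview re-checks eligibility, but against the criteria above.

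Task 2.6 compares the dementias with the control volunteers and the groups with one another. It has no rule for a control who scores as impaired.

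**The concern.** Patients and controls are classified on unequal evidence. A patient has a specialist diagnosis. A control has only the absence of one, and no examination before entry is described. In people over 60, having no diagnosis is not the same as having normal cognition.

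Cognitive state is the axis on which the WP2 groups are meant to differ, and amnesic MCI is itself a study group. A person with unrecognised MCI meets the control criteria as written, which would blur the contrast between MCI and controls. The same 30 controls are the reference for every patient group, so a problem in that group is not confined to one comparison. The expected harm is lost sensitivity: real microbiota differences become harder to see.

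**Working it through.** **Following the rule as written.** A volunteer over 60 with unrecognised MCI and none of the listed medicines or gut conditions meets Task 2.2. At the Task 2.3 interview the eligibility re-check finds nothing, because the criteria contain no cognitive threshold. The CDR and MMSE are recorded with no consequence. In Task 2.6 the person is analysed as a control. No step in the plan stops this.

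**The plan's own figure.** Task 2.1 takes 25 per group from a cited study and adds 5, giving 30. That sum is right. It cannot be reproduced further, because WP2 states no endpoint, effect size, SD, alpha or power.

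**Illustration of scale.** All inputs except the 25 and the 30 are assumptions:
- Two-sided alpha 0.05 and a two-sample t-test, standing in for the composition analysis.
- Standardised difference d = 0.81, which is what 25 per group detects with 80% power.
- A share f of controls is impaired, lying a fraction k of the way from a true control to the patient group. The within-group SD is treated as unchanged.

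The difference shrinks to d(1 − kf). With n = 30 per group the noncentrality is d(1 − kf)√(n/2), on 58 degrees of freedom. With no contamination it is 0.81 × √15 = 3.137, and power is 87%.

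If impaired controls are instead removed without replacement, m = 30(1 − f) remain. The noncentrality is then 0.81√(30m/(30 + m)), on 28 + m degrees of freedom.

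| f | impaired of 30 | keep, k = 1: noncentrality, power | keep, k = 0.5: noncentrality, power | remove: m, noncentrality, power |
|---|---|---|---|---|
| 10% | 3 | 2.823, 79% | 2.980, 83% | 27, 3.053, 85% |
| 20% | 6 | 2.510, 69% | 2.823, 79% | 24, 2.958, 83% |
| 30% | 9 | 2.196, 58% | 2.667, 75% | 21, 2.847, 80% |

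At f = 5% the difference is 0.81 × 0.95 = 0.770 for k = 1 (power 83%) and 0.81 × 0.975 = 0.790 for k = 0.5 (power 85%), so the loss is small.

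**When removal pays.** Removal has the larger noncentrality when √(30m/(30 + m))/√15 exceeds 1 − kf. For f = 10%, 20% and 30% the ratio is 0.973, 0.943 and 0.908. The break-even k is therefore 0.027/0.10 = 0.27, 0.057/0.20 = 0.29 and 0.092/0.30 = 0.31. Removal wins if impaired controls lie more than about 30% of the way to the cases. If they do not resemble cases at all (k = 0), it costs 2, 4 or 7 points from 87%. Replacing those removed avoids that cost. The comparison assumes that the CDR and MMSE identify impaired controls correctly.

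**The case against.** A reader might infer that impaired people do enter the control group, that every contrast is pulled towards zero, and that power falls to about half. The documents do not support that reading.

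- They show that entry is permitted, not that it occurs. They give no rate of undiagnosed impairment, and do not say how many relatives or members of the public had been examined.
- Full dilution of every contrast would need an impaired control to resemble all the disease groups at once. WP2 compares those groups with each other, so it does not presume that they share a profile. Full resemblance is most plausible for MCI.
- A power of 50% arises only at 30% contamination, full resemblance and 25 per group, that is, with all five spare participants lost from each group. The plan recruits 30.
- The stated objective names four dementias against controls. MCI against controls is only implied, by the between-group comparisons in Task 2.6.

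There is also some mitigation. The instruments are labelled as screening, and descriptives are promised for each group, so impaired controls would be visible. A methodology specialist is to review the analysis. Finally, selecting controls on the CDR and MMSE makes the groups differ on those scales by construction and narrows the range for analyses relating microbiota to cognition.

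All of this limits the size and reach of the point, and the last item must be handled in the fix. It does not close the gap: a screen with no consequence excludes nobody, and a decision taken after the microbiota data are seen is not a pre-specified definition of a control.

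**Conclusion.** The point holds as a gap in the definition of the WP2 control group. As far as cognition is concerned, a control is anyone over 60 without a diagnosed significant neurological disease, and nothing later in the plan corrects that. Any contamination would bear first on MCI against controls. It would bear on each dementia comparison in proportion to how far impaired controls resemble that group.

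The size is unknown. Under the stated assumptions, the loss at 30 per group runs from a few points (87% to 83% or 85% at 5% contamination) to 29 points (87% to 58% at 30% with full resemblance). These figures show scale and do not estimate the power of the study. Comparisons between patient groups are untouched, as is the randomised comparison in WP3. The change is worth making because the data needed are already collected.

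**What to change.** In Task 2.2, count a volunteer as a healthy control only if, at the Task 2.3 interview, the CDR global score is 0 and the MMSE is normal for age and education against a named norm. Choose the norm and cut-off before any microbiota data are seen; the documents name none. Replace volunteers who fail. There is time for this, since Task 2.5 ships samples only after recruitment ends. State in Task 2.6 how those who fail are handled.

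Task 2.2 mixes future and past tense, so recruitment may already be complete. In that case, apply the same two-part definition to form the main control group and report all recruited controls as a sensitivity analysis.

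The cost is a few replacement controls or a slightly smaller group. Differences between controls and patients on the CDR and MMSE become partly true by construction, so report them as descriptive only. Keep all volunteers, including those who fail the definition, in the analyses relating microbiota to cognition.

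### Do the stated sample-size inputs for the probiotic trial contradict the 25 patients per group that the plan derives from them?

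*Combined protocol and SAP*

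**What the plan says.** The sample-size paragraph in WP3, Task 3.1 is the only such calculation for the randomised trial. It says "we used the standard formula suggested for clinical trials", with a "type one error(a) of 0.05" and a type II error of 0.20, that is 80% power. The effect assumptions are given as "We used 1.3 as SD and 1.1 as the difference in mean (d) of MMSE as key variable". The result is "Accordingly, we needed 25 persons in each group", followed by "Assuming 5 dropouts in each group, the final sample size was determined to be 30 persons per group". Earlier in the same task the allocation is described as "30 will ingest the probiotic mixture and 30 will ingest placebo", so 60 in total. Task 3.6 names Student's t-test among the methods for comparing the groups.

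The paragraph does not say which formula was used, whether the test is one- or two-sided, or whether the SD and the difference were rounded for printing.

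**The concern.** The paragraph presents 25 as the direct output of four stated inputs, and attrition is added only afterwards, so dropouts cannot explain the figure. Anyone who puts the inputs into the usual two-sample formula gets 22, or 23 with the t-test. The figure of 25 does appear if power is raised to 85%, or if the SD is about 1.39 or the difference about 1.03 at 80% power, but the plan states none of these. That suggests that an input or the result was misreported.

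If so, a reader could not tell what power the trial was designed to have. The attrition margin would also be wrong: if 23 completers suffice, 30 per group can lose 7 patients, not 5, and still keep 80% power.

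**Working it through.** **Inputs** (Task 3.1): alpha 0.05, power 0.80, SD 1.3, difference 1.1, allocation 1:1. Two-sided testing is my assumption, because the plan does not state it. The standardised difference is 1.1/1.3 = 0.846.

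**Direct recalculation, inputs taken as exact.**

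- Normal formula: n = 2 × (1.960 + 0.842)² × SD² / difference² = 2 × 7.849 × 1.69 / 1.21 = 21.92, so 22 per group.
- Two-sample t-test (noncentral t): 22.93, so 23 per group.
- One-sided normal formula: 17.27, so 18, which is further from 25.
- Normal formula at 85% power: 25.08.

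The plan's 25 is not reproduced exactly from the printed values. It is 3 above the normal formula (3/22 = 14%) and 2 above the t-test (2/23 = 9%).

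**Could rounding of the printed inputs explain it?** An SD printed as 1.3 may lie anywhere from 1.25 to 1.35, and a difference printed as 1.1 from 1.05 to 1.15. Two-sided, at 80% power:

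| SD | Difference | Normal formula | t-test |
|---|---|---|---|
| 1.25 | 1.15 | 18.5 | 19.6 |
| 1.30 | 1.10 | 21.9 | 22.9 |
| 1.33 | 1.08 | 23.8 | 24.8 |
| 1.34 | 1.07 | 24.6 | 25.6 |
| 1.35 | 1.05 | 25.9 | 26.9 |

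The value 25 lies inside both ranges. It results from SD 1.34 and difference 1.07 with the normal formula (24.6, rounded up), and from SD 1.33 and difference 1.08 with the t-test (24.8, rounded up). The figures of 1.39 and 1.03 come from moving one input at a time with the normal formula. Moving both slightly is enough.

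**What the planned numbers deliver on the printed inputs (two-sided).**

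| Completers per group | Power, t-test | Power, normal |
|---|---|---|
| 22 | 78.3% | 80.1% |
| 23 | 80.1% | 81.8% |
| 25 | 83.4% | 84.9% |
| 30 | 89.7% | 90.6% |

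**Dropout step.** 25 + 5 = 30 per group, and 2 × 30 = 60, which agrees with the total at the start of Task 3.1. The allowance is 5/30 = 16.7%. On the printed inputs and the t-test, 30 per group would keep 80% power with 30 − 23 = 7 losses (7/30 = 23.3%).

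**The case for a change.** The strongest case for a correction is that a power statement should be reproducible from what is printed, and this one is not. The paragraph refers to a standard formula, and the textbook version gives 22. No margin, correction or rounding is mentioned that would bridge the gap, and rewording one paragraph costs almost nothing. The same task also has a contingency of 5 to 10 further patients per group, without saying whether these include the 5 dropouts.

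Part of this stands: the formula, the sidedness and the unrounded SD and difference are not given, so a reader cannot derive 25 with certainty. Rounding is a possible explanation, not an established one, since the unrounded values are not in the documents.

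The stronger claims do not stand. It does not follow that an input or the result must be wrong, because values consistent with the printed ones give 25. Nor is the dropout allowance misreported. Assuming 5 losses is a planning assumption, not a claim that 5 is the most the trial could bear; that 30 per group could absorb 7 only shows the plan to be a little more protective than it says. Treatment lasts 24 weeks, whereas the cited result for the mixture was at 12 weeks, but this has no bearing on whether the inputs lead to 25. If longer treatment brought more losses, the extra room would help. Writing 22 or 23 into the protocol as the requirement could even replace a correct figure with one based on rounded inputs.

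**Conclusion.** No change is needed. With the printed inputs taken as exact and a two-sided test assumed, the requirement is 22 or 23 per group against the stated 25. The discrepancy of 2 to 3 patients is within what rounding of the SD and the difference can produce, and it is conservative. On the plan's own assumptions 25 completers per group give about 83% to 85% power and 30 give about 90%, so the stated 80% is delivered. The recruitment target of 30 per group is consistent throughout Task 3.1.

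What remains is missing detail about the formula, the sidedness and the rounding. Supplying it would leave enrolment, analysis and interpretation as they are. This conclusion concerns the arithmetic only: it takes the SD of 1.3 and the difference of 1.1 as given and does not judge whether they are realistic for this population.
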